3.1. Randomization

Approximately 140 participants will be randomized 1:1:1:1 (ie, placebo or povorcitinib 15, 45, or 75 mg) with approximately 35 participants per group.

Participant randomization will be stratified based on IGA score on Day 1 (3 vs 4).

3.2. Control of Type I Error

The overall significance level for efficacy analysis will be 0.05 for 2-sided tests.

A set of hypotheses corresponding to the treatment comparisons between povorcitinib 15, 45, or 75 mg and placebo will be tested in fixed sequential:

- H1: Povorcitinib 75 mg is not equal to placebo in achieving ≥ 4-point improvement in Itch NRS score at Week 16
- H2: Povorcitinib 45 mg is not equal to placebo in achieving ≥ 4-point improvement in Itch NRS score at Week 16
- H3: Povorcitinib 15 mg is not equal to placebo in achieving ≥ 4-point improvement in Itch NRS score at Week 16

Hypothesis 2 will only be tested if H1 is rejected; testing for H3 will be implemented only if H1 and H2 are rejected.

3.3. Sample Size Considerations

In order to provide a safety database and adequate power for efficacy analysis, the total sample size for the study is 140 participants randomized in a 1:1:1:1 ratio to povorcitinib 15, 45, or 75 mg or placebo groups and stratified by IGA score on Day 1 (3 vs 4). The sample size calculation is based on Fisher's exact test for the statistical comparison on the primary efficacy endpoint, ie, the proportion of participants achieving \geq 4-point improvement in Itch NRS at Week 16. Based on the results from a Phase 2 trial of nemolizumab (Stander et al 2020), the response rate is assumed to be 50% for the povorcitinib 45 and 75 mg groups and 15% for the placebo group. Using a 2-sided alpha of 0.05, 35 participants per group will have 85% power to detect such a difference between either one of the 3 active treatment groups and the placebo group.

3.4. Schedule of Assessments

Refer to Protocol Amendment 2 dated 06 MAY 2022 for a full description of all study procedures and assessment schedules for this study.

4. DATA HANDLING DEFINITIONS AND CONVENTIONS

4.1. Scheduled Study Evaluations and Study Periods

4.1.1. Day 1

Day 1 is the date that the first dose of study drug (povorcitinib) or placebo is administered to participants. The treatment groups are described in Table 2 for each period, as well as in Section 5.2.

Treatment Period	Treatment Group	Day 1
PC period (Up to Week 16)	Placebo Povorcitinib 15 mg Povorcitinib 45 mg Povorcitinib 75 mg	The day of the first dose of study drug (povorcitinib or placebo) administered to participants in the PC period.
Extension period (Week 16 through Week 40)	Week 16 responder: Placebo to povorcitinib Povorcitinib Povorcitinib Povorcitinib Week 16 nonresponder: Placebo to povorcitinib Povorcitinib Povorcitinib Povorcitinib Povorcitinib	The day of the first dose of study drug (povorcitinib or mg) administered to participants in the extension period.
Overall period (Up to Week 40)	Povorcitinib 45 mg Povorcitinib 75 mg Note: These groups consist of participants who took only povorcitinib 45 or 75 mg during the study.	The day of the first dose of study drug (povorcitinib 45 or 75 mg) administered to participants in the PC period.

Table 2:Definition of Day 1

For randomized participants not treated with any study drug, Day 1 is defined as the day of randomization.

4.1.2. Study Day

If a visit/reporting date is on or after Day 1, then the study day at the visit/reporting date will be calculated as

Day # = (visit/reporting date - Day 1 date + 1).

If the visit/reporting date is before Day 1, then the study day at the visit/reporting date will be calculated as

Day # = (visit/reporting date - Day 1 date).

A study day of -1 indicates 1 day before Day 1.

4.1.3. Baseline Value

For efficacy and safety evaluations in the PC period, baseline is the last nonmissing measurement obtained before or on the first administration of povorcitinib or placebo in the PC period.

• For randomized participants not treated with any study drug, baseline is defined as the last nonmissing assessment before or on the day of randomization for all parameters.

Note that for participants who entered the extension period, baseline is defined as follows:

- For efficacy evaluation in the extension period, baseline is the last nonmissing measurement obtained before the first administration of povorcitinib or placebo in the PC period (hereafter referred to as PC baseline).
- For safety evaluation in the extension period, baseline is the last nonmissing measurement obtained before the first administration of study drug in the extension period (hereafter referred to as extension baseline).

When scheduled assessments and unscheduled assessments occur on the same day and the time of the assessment or time of first dose is not available, use the following convention to determine baseline:

- If both a scheduled and an unscheduled visit are available on the day of the first dose and the time is missing, use the scheduled assessment as baseline.
- If all scheduled assessments are missing on the day of the first dose and an unscheduled assessment is available, use the unscheduled assessment as baseline.

Table 3 provides an outline of baseline definitions for efficacy and safety evaluation in each period.

Treatment Period	Treatment Group	For Efficacy Evaluation	For Safety Evaluation
PC period (Up to Week 16)	Placebo Povorcitinib 15 mg Povorcitinib 45 mg Povorcitinib 75 mg	PC baseline	PC baseline
Extension period (Week 16 through Week 40)	Week 16 responder: Placebo to povorcitinib Povorcitinib Povorcitinib Povorcitinib Week 16 nonresponder: Placebo to povorcitinib Povorcitinib Povorcitinib Povorcitinib Povorcitinib	PC baseline	Extension baseline

Table 3:Definitions of Baseline

Treatment Period	Treatment Group	For Efficacy Evaluation	For Safety Evaluation
Overall period (Up to Week 40)	Povorcitinib 45 mg Povorcitinib 75 mg Note: These groups consist of participants who took only povorcitinib 45 or 75 mg during the study.	Not applicable	PC baseline

Table 3:Definitions of Baseline (Continued)

4.1.4. Handling of Missing and Incomplete Dates

In general, values for missing dates will not be handled unless methods for handling missing dates are specified in this section or relevant sections. The original reported dates collected on the eCRF should be used in all relevant listings. The following rules will be used for handling partial dates for analyses requiring dates.

When calculating the time since diagnosis of PN, a partial PN diagnosis date will be handled as follows in the calculation:

- If only the day is missing, then the first day of the month will be used.
- If both the month and day are missing, then 01 JAN of the year will be used.
- If the diagnosis date is completely missing, then the time since diagnosis will not be calculated.

When the date of the last dose in a specific period is used in deriving variables, such as duration of treatment or TEAE flag, a missing or partial date of the last dose will be handled as follows:

- If only the day is missing, then the earlier date of the last day of the month or the date that the participant discontinued treatment will be used.
- If both the month and day are missing, then the earlier date of 31 DEC of the year or the date that the participant discontinued treatment will be used.
- Otherwise, the date that the participant discontinued treatment will be used as the date of the last dose.

4.2. Variable Definitions

The following variable will only be calculated if not reported on the eCRF.

4.2.1. Body Mass Index

Body mass index will be calculated as follows:

Body mass index $(kg/m^2) = [weight (kg)] / [height (m)]^2$.

4.2.2. Prior and Concomitant Medication

Prior medication is defined as any nonstudy medication started before the first dose of povorcitinib or placebo in the PC period.

For the PC period, concomitant medication is defined as any nonstudy medication that is started accordingly:

- Before the date of first administration of povorcitinib or placebo in the PC period and is ongoing or ends on/after the date of first study drug administration in the PC period, OR
- On/after the date of first administration of povorcitinib or placebo in the PC period, and before the date of first administration of povorcitinib in the extension period for participants who enter the extension period.

For the extension period, concomitant medication is defined as any nonstudy medication that is started accordingly:

- Before the date of first administration of povorcitinib in the extension period and is ongoing throughout the study or ends on/after the date of first study drug administration in the extension period, OR
- On/after the date of first administration of povorcitinib in the extension period.

For the overall period, concomitant medication is defined as any nonstudy medication that is started accordingly:

- Before the date of first administration of povorcitinib in the PC period and is ongoing throughout the study or ends on/after the date of first study drug administration in the PC period, OR
- On/after the date of first administration of povorcitinib in the PC period.

A prior medication could also be classified as "both prior and concomitant medication" if the end date is on or after first dose of povorcitinib or placebo in the PC period. In the listing, it will be indicated whether a medication is only prior, only concomitant, or both prior and concomitant.

For the purposes of analysis, all medications will be considered concomitant medications unless the medications can unequivocally be defined as not concomitant.

5. STATISTICAL METHODOLOGY

5.1. General Methodology

Unless otherwise noted, SAS[®] software (SAS Institute Inc, Cary, NC; v9.1 or later) will be used for the generation of all tables, graphs, and statistical analyses. Descriptive summaries for continuous variables will include, but not be limited to, the number of observations, mean, standard deviation, median, minimum, and maximum. Descriptive summaries for categorical variables will include the number and percentage of participants in each category.

5.2. Treatment Groups

This is a randomized, double-blind, placebo-controlled, dose-ranging study followed by a single-blind extension period. Table summaries, unless otherwise indicated, will present data by treatment group. The results will be summarized and presented separately for the PC period, the extension period, and overall period (for safety only) unless otherwise specified.

For the PC period, the treatment groups will be placebo and povorcitinib 15, 45, and 75 mg.

For the extension period, participants will be grouped into 2 cohorts (Week 16 responders and Week 16 nonresponders); these 2 cohorts will then be separated into the following subgroups, per the treatments they received during the PC and extension periods:

- Week 16 responders:
 - Placebo to povorcitinib
 - Povorcitinib 15 to
 - Povorcitinib
 - Povorcitinib to
- Week 16 nonresponders:
 - Placebo to povorcitinib
 - Povorcitinib 15 to
 - Povorcitinib to
 - Povorcitinib

Safety results will be summarized and presented by the following treatment groups who took same dose across study:

- Povorcitinib 45 mg will consist of participants who took only 45 mg during the overall period (including participants who received at least 1 dose of during both the PC and extension periods, and participants who received at least 1 dose of 45 mg during the PC period and discontinued during the PC period).
- Povorcitinib 75 mg will consist of participants who took only 75 mg during the overall period (including participants who received at least 1 dose of during both the PC and extension periods, and participants who received at least 1 dose of 75 mg during the PC period and discontinued during the PC period).

5.3. Analysis Populations

5.3.1. All-Randomized Population

The all-randomized population will include all participants who were randomly assigned to receive placebo or povorcitinib.

5.3.2. Intent-to-Treat Population

All participants who were randomized will constitute the ITT population. Treatment groups for this population will be defined according to the treatment assignment at the time of randomization regardless of the actual study treatment the participant might apply during their participation in the PC period.

The ITT population will be used for the summary of demographics, baseline characteristics, participant disposition, and analyses of all efficacy data in the PC period and the overall period.

5.3.3. Safety Population

The safety population will include all participants who received at least 1 dose of povorcitinib or placebo during the PC period. Treatment groups for this population will be determined according to the actual treatment the participant receives on Day 1 in the PC period regardless of assigned study drug treatment.

All safety analyses for the PC period and the overall period will be conducted using the safety population.

5.3.4. Extension Evaluable Population

All analyses for the extension period will be conducted with the extension evaluable population, which includes all participants who received at least 1 dose of povorcitinib during the extension period.

6. **BASELINE, EXPOSURE, AND DISPOSITION**

Appendix A provides a list of data displays. Sample data displays are included in a separate document.

6.1. Demographics, Baseline Characteristics, and Disease History

The demographics, baseline characteristics, and disease history will be summarized by treatment groups and overall.

6.1.1. Demographics and Baseline Characteristics

The following demographics will be summarized for the ITT and the extension evaluable populations: age; age group (< 65 and \geq 65 years); sex; race; ethnicity; weight; height; BMI; and BMI category (< 25 kg/m², \geq 25 to < 30 kg/m², \geq 30 to < 40 kg/m², \geq 40 to < 50 kg/m², and \geq 50 kg/m²).

The following demographic will be summarized for the ITT population only: tobacco use (never used, current user, or former user).

6.1.2. Baseline Disease Characteristics and Disease History

The following baseline disease characteristics and disease history will be summarized for all participants in the ITT population, including, but not limited to:

- Disease duration (years)
- Fitzpatrick scale skin type (Type I/II/III/IV/V/VI)
- PN family history
- Prior therapy for PN (yes/no)
- Prior therapeutic response (complete, good, limited improvement, lack of efficacy)
- Selected comorbidities

Note: Disease duration (years) will be calculated as follows:

Disease duration (years) = (date of randomization – date of initial PN diagnosis + 1) / 365.25.

6.1.3. Medical History

For participants in the ITT population, medical history will be summarized by assigned treatment group. This summation will include the number and percentage of participants with medical history for each body system/system organ class as documented on the eCRF.

6.2. Disposition of Participant

The number of participants enrolled by country and/or site will be provided by treatment group and overall.

The following categories will be summarized by treatment group and overall for the ITT population in the PC period:

- Number (%) of participants who were randomized
- Number (%) of participants who were treated in the double-blind PC period
- Number (%) of participants who completed treatment in the PC period through Week 16
- Number (%) of participants who discontinued treatment with a primary reason for discontinuation in the PC period
- Number (%) of participants who withdrew from the study with a primary reason for withdrawal in the PC period
- Number (%) of participants who withdrew from study due to COVID-19 in the PC period

The following categories will be summarized by treatment group and overall for the extension evaluable population in the extension period:

- Number (%) of participants who were treated in the extension period
- Number (%) of participants who completed treatment in the extension period
- Number (%) of participants who discontinued the study treatment with a primary reason for discontinuation in the extension period
- Number (%) of participants who completed the study
- Number (%) of participants who withdrew from the study with a primary reason for withdrawal in the extension period
- Number (%) of participants who withdrew from study due to COVID-19 in the extension period

6.3. **Protocol Deviations**

Protocol deviations recorded will be summarized and listed for the ITT and extension evaluable populations, as well as the individual protocol deviations indicated on the eCRF.

6.4. Exposure

For participants in the safety population in the PC period and the extension evaluable population in the extension period, as well as for participants who only took povorcitinib 45 or 75 mg during the overall period, the exposure to the study drug will be descriptively summarized by treatment group as follows:

• **Duration of treatment with povorcitinib (days)**: Date of last dose of study drug in the specific period – date of first dose of study drug in the specific period + 1.

Note that the date of first and last dose of the study drug in each period are defined in Table 4.

Treatment Period Treatment Group First Dose Date Last Dose Date Placebo PC period Date of first dose of Date of last dose of study Povorcitinib 15 mg drug administration in the study drug Povorcitinib 45 mg administration in the PC period Povorcitinib 75 mg PC period Date of first dose of Date of last dose of study Extension period Week 16 responders: Placebo to povorcitinib study drug drug administration in the Povorcitinib 15 to administration in the extension period Povorcitinib extension period Povorcitinib Week 16 nonresponders: Placebo to povorcitinib Povorcitinib 15 to Povorcitinib 0 Povorcitinib Povorcitinib 45 mg Overall period Date of first dose of Date of first dose of study Povorcitinib 75 mg drug administration study drug administration in the during the overall period PC period Note: These groups consist of participants who took only povorcitinib 45 or 75 mg during the study.

Table 4:Definition of First and Last Dose Date

For participants in the safety population in the PC period and the extension evaluable population in the extension period, the average daily dose of povorcitinib and total actual dose of povorcitinib administered will be summarized by treatment groups as follows:

- Average daily dose of povorcitinib (mg/day): Total actual povorcitinib dose taken in the specific period (mg) / [duration of treatment with povorcitinib in the specific period (days) – number of interrupted days with povorcitinib in the specific period].
- Total actual dose of povorcitinib administered (mg): (Total number of tablets dispensed in the specific period total number of tablets returned in the specific period) × 15 (mg/tablet) × p_T ,

where p_T denotes the proportion of povorcitinib among the 5 tablets taken daily (ie, $p_T = 0$ (0/5) for placebo group, 1/5 for povorcitinib 15 mg group, 3/5 for povorcitinib 45 mg group, and 5/5 for povorcitinib 75 mg group).

The total number of tablets dispensed and returned in each period is based on information entered on the Drug Accountability eCRF. Should the dispensed drug not be returned, the actual dose taken, starting from the dispense date of the unreturned drug, will be imputed by the dose taken per the Compliance eCRF.

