9.1. General Considerations

The analyses in this section will be provided for the safety population in the PC period, the extension evaluable population in the extension period, and for participants who took only povorcitinib 45 or 75 mg during the overall period, unless otherwise specified. Summary tables may be replaced with listings when appropriate; for instance, an AE frequency table may be replaced with a listing if it only contains a few unique preferred terms reported on relatively few participants.

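### SAP Table 4 defines the overall-period last dose date as a first dose date, so overall-period exposure is 1 day for every participant as written (minor; a one-word fix)

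*SAP*

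**What the plan says.** **Duration.** SAP 6.4 takes duration as "Date of last dose of study drug in the specific period" minus the corresponding first dose date, plus 1, and states that Table 4 defines both dates for each period.

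**Table 4.** The extracted text interleaves the columns, but the cells can be separated.

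- PC row: "Placebo PC period Date of first dose of Date of last dose of study". The second date cell is the last dose in that period.
- Extension row: the same pattern, with the last dose in the second date cell.
- Overall-period row: "Overall period Date of first dose of Date of first dose of study". The first date cell is the first dose in the PC period. The second, under the last-dose heading, is the first dose during the overall period.

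**Missing dates.** SAP 4.1.4 gives rules for incomplete last dose dates: "When the date of the last dose in a specific period is used in deriving variables, such as duration of treatment".

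**Who is in the overall-period groups.** SAP 5.2 says: "Povorcitinib 45 mg will consist of participants who took only 45 mg during the overall period". The group includes "participants who received at least 1 dose of 45 mg during the PC period and discontinued during the PC period", and the 75 mg group is built in the same way. SAP 9.1 plans the safety outputs "for participants who took only povorcitinib 45 or 75 mg during the overall period, unless otherwise specified". SAP 5.3.3 names the population: "All safety analyses for the PC period and the overall period will be conducted using the safety population". SAP sections 1 and 3 say that the extension dose is set by Itch NRS and IGA response at Week 16.

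**The concern.** Table 4 supplies the operative definition for the duration formula. If its last-dose cell names a first dose, the formula has no end date and returns the same value for everyone, however long they were treated.

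The output at stake is Table 3.1.1.3, the only planned exposure summary that spans both periods. SAP 6.4 plans average daily dose and total dose only for the PC and extension periods, so duration is the only exposure measure defined for that table. A reader of the overall-period safety tables would look there for the length of exposure behind the event counts.

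A smaller reporting question concerns the same tables. The statement of who is in the groups and the statement that Week 16 response sets the extension dose stand in different sections, and no single sentence joins them.

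**Working it through.** **Inputs**

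- Duration = last dose date − first dose date + 1 (SAP 6.4).
- Overall-period first dose date: first dose in the PC period (SAP Table 4).
- Overall-period last dose date as written: first dose during the overall period (SAP Table 4).
- Day 1 of the overall period: the day of first dosing in the PC period (SAP Table 2).
- Planned treatment: 16 weeks plus 24 weeks (Protocol Table 2). Visit window at Week 40: ±3 days (Protocol Table 4).

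**Step 1: the plan's own figure.** 16 + 24 = 40 weeks, as the protocol states, and 40 × 7 = 280 days.

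**Step 2: is this an extraction artefact?** No. The PC and extension rows went through the same broken layout and keep the word *last* in the second date cell. In the overall-period row both cells say *first*, and *last* does not appear.

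**Step 3: duration as written.** Members of these groups took their first overall-period dose in the PC period, so the two Table 4 dates coincide. Setting the first dose to day 1, duration = 1 − 1 + 1 = 1 day for every participant.

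**Step 4: duration with the last dose in the cell**

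| Participant | Last dose on day | Duration, corrected | Duration, as written |
|---|---|---|---|
| Completes 40 weeks | 280 | 280 − 1 + 1 = 280 | 1 |
| Completes, edges of the Week 40 window | 277 to 283 | 277 to 283 | 1 |
| Stops in the PC period, for example day 56 | 56 | 56 − 1 + 1 = 56 | 1 |

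**Step 5: what else uses the cell**

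- PC and extension durations use their own rows, which are correct.
- Average daily dose and total dose are planned only for those two periods. Appendix A lists compliance tables only for the safety and extension evaluable populations, with no separate overall-period table.
- The general TEAE definition in SAP 9.2.1 refers to the last dose, but the window for participants who took only 45 or 75 mg is stated separately and runs to the end of safety follow-up. It does not draw on Table 4.
- No efficacy test uses the cell.

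**Step 6: group membership, by reading the sections together.** A participant who stops in the PC period enters the overall-period group without a Week 16 dose decision. A participant who enters the extension stays in the group only if the dose is unchanged, and that dose follows from Week 16 response. For those participants, membership therefore depends on an outcome observed after randomisation. The pairing of response with extension dose is redacted, so the share of each arm retained cannot be derived from the documents, and no size is given here.

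**The case against.** The strongest reply is that nobody would be misled. The column is headed as the last dose, the formula calls for the last dose, the other two rows are right, and SAP 4.1.4 has rules for an incomplete last dose date used for duration. A programmer would probably correct the cell silently, and a table showing 1 day for everyone would be noticed at once. This stands as an argument about weight and is why the point is minor. It does not make the definition right: 6.4 expressly hands the definition to Table 4, and 4.1.4 covers missing or partial dates without overriding it.

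Two stronger readings are tempting, and the documents support neither.

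- *The rule cannot be programmed, or the trial will report 1 day of exposure.* The rule can be programmed; it returns 1 day. The figure follows from a literal reading. It is not a forecast of what will be reported.
- *The overall-period groups are selected without disclosure, which distorts the safety comparison of 45 mg with 75 mg.* Group composition, including the retention of PC-period discontinuers, is stated in 5.2. The restriction to a single dose is repeated in notes to SAP Tables 2 to 4, in 9.1 and in the Appendix A titles. The dependence of the extension dose on Week 16 response is stated in sections 1 and 3. No randomised contrast between the two doses is planned from these tables. Discontinuation in the PC period is already planned over the full arms (Table 3.2.16.x and section 6.2). Table shells, where footnotes would appear, are in a separate document, so a missing footnote cannot be established. Any percentage put on the selection would rest wholly on assumed rates. SAP 5.3.3 does not conflict with 5.2 either: one names the population, the other the groups within it.

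**Conclusion.** The overall-period last dose date in SAP Table 4 is wrong as written, and the error is minor. Followed literally, it gives 1 day for every participant in Table 3.1.1.3, against up to 280 days planned. This needs no assumption beyond the SAP formula, Table 4 and the protocol's treatment length. The effect is confined to one descriptive duration.

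The remark on group membership is an optional reporting note, not an error in the SAP. That membership depends on Week 16 response, for those who enter the extension, follows from unredacted text. How many participants this removes from each arm is not known.

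**What to change.** In the overall-period row of SAP Table 4, replace *first* with *last* in the Last Dose Date cell, so that it means the last dose of study drug taken during the overall period. This is one word. It changes no data collection, no tested hypothesis and no other planned table.

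Optionally, add one sentence to SAP 5.3.3 or a footnote to the overall-period tables. It would say that the 45 mg and 75 mg groups are the subset of the safety population defined in 5.2, that for participants entering the extension membership depends on Week 16 response, and that the two columns are not a randomised dose comparison. The cost is one line of text.
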